The Innate Central Nervous System Immune Response to an
Experimental Immune Challenge in People With Fibromyalgia

Protocol

NCT04263454

Version Date: 01/06/2021

[name], Professor, Principal Investigator
University of Alabama at Birmingham
[name]

Methods

Design

This study utilized a mixed (group-by-time) design to compare changes in brain metabolites before and after an experimental endotoxin challenge between FM and HC groups. Participants underwent an MRI 1.5 hours before receiving the endotoxin infusion, and 4 hours after. The following were measured with EPSI in 47 brain regions as primary outcomes: brain temperature, CHO, MI, and NAA.

Procedures

Study procedures were approved by the University of Alabama at Birmingham (UAB) Institutional Review Board and conducted in accordance with the Declaration of Helsinki. Participants provided written informed consent prior to any procedures. A payment of \$50 was provided following completion of the screening visit, and \$600 was provided for the experimental session. Screening and experimental sessions were performed at the Clinical Research Unit (CRU) located at UAB Hospital. Brain imaging was conducted at the UAB Civitan International Imaging Laboratory (CINL). During the experimental session, participants were transported between locations via rideshare transportation.

Participants

Women with FM aged 18-55 and healthy age-matched women were recruited from the Birmingham community via online advertisements on the UAB Clinical Trials website. Our laboratory maintains a database of individuals who have indicated an interest in research, from which additional participants were contacted. Participants in the FM group met the revised diagnostic criteria by the American College of Rheumatology,^{1,39,40} endorsed at least eleven out of nineteen positive tender points on a physical exam, and reported an average daily widespread

pain severity of at least 6 on a 0-10 scale. HCs reported average daily pain of 1 out of 10 or less. The following exclusion criteria were applied to both groups: i) MRI contraindications; ii) ECG abnormalities (QTc>450ms, QRS>120ms); iii) fever >99.0 °F; iv) hypotension or hypertension (systolic blood pressure outside of 100-140 range, diastolic blood pressure outside of 60-90 range); v) resting heart rate <55bpm; vi) body mass index (BMI) outside of 19.0-39.9 range; vii) current smoker (within 12 months of study); viii) pregnant, planning to become pregnant, or breastfeeding; ix) high alcohol consumption (>1 drink/day or >4 drinks on a single occasion per week); x) use of illicit substances within six months of participation; xi) vaccination within four weeks of participation; xii) viral or bacterial illness requiring medical attention or antibiotics within three months of participation; xiii) concurrent participation in another research study; xiv) surgical procedure within three months of participating; xv) history of rheumatologic or autoimmune disease (e.g., multiple sclerosis, systemic lupus erythematosus, rheumatoid arthritis, Hashimoto's thyroiditis); xvi) other major medical conditions (e.g., cancer, blood or clotting disorder, HIV, Hepatitis C infection, diabetes); xvii) regular use of anti-inflammatory or immunomodulatory drugs, xviii); current use of opioid analgesics; xix) Hospital Anxiety and Depression Scale (HADS)⁴¹ depression total score ≥13; xx) values outside clinical reference ranges on tests of renal function, tri-iodothyronine, thyroxine, thyroid stimulating hormone, complete blood count with differential, and 25-hydroxy vitamin; xxi) detectable rheumatoid factor or antinuclear antibody, xxii) erythrocyte sedimentation rate >60 mm/h, xxiii) high sensitivity C-reactive protein (hsCRP) >10 mg/L, and xiv) ongoing litigation or worker's compensation claim.

Screening visit

Initial inclusion and exclusion criteria, including medical history, ACR criteria, HADS score, and MRI safety, were established via brief phone calls. Interested individuals presented in person to the CRU to complete the remaining screening procedures. Participants underwent a urine pregnancy test and ECG. A tender point exam was administered by applying up to 4kg pressure at a rate of 1kg per second to the nineteen tender points established by the ACR³⁹ with an FPK20 manual algometer (1cm diameter; Wagner Instruments, Greenwich, CT). Thirty-three cc blood was collected by research nurses and transported to the UAB Hospital laboratory for processing and confirmation of inclusion/exclusion criteria. Participants also completed the Brief Pain Inventory (BPI)⁴² and Fibromyalgia Impact Questionnaire⁴³ (FIQ, FM participants only).

Experimental Session

Participants presented to the UAB CRU and underwent a repeat ECG for safety and were then transported to the CINL for brain imaging. Participants returned to the CRU, where endotoxin from *E. coli* (0.4ng/kg body weight, N=14, or 0.3ng/kg body weight, N=11) was administered via infusion over 30 minutes. The endotoxin dose was reduced to 0.3ng/kg after several participants experienced adverse events following 0.4ng/kg infusions. Two standardized meals of 834 kcal and 508 kcal were provided to participants prior to the first MRI session and 1 hour after the endotoxin infusion, respectively.

Image Acquisition

MRI data were collected on a Siemens Magnetom Prisma 3-Tesla scanner with 20-channel head coil. Participants laid supine, were provided with hearing protection, and were instructed to keep their eyes closed during the acquisition. A T1-weighted structural brain scan

was collected with a magnetization-prepared rapid gradient echo (MPRAGE) sequence with the following parameters: TR: 2000 ms, TE: 2.51 ms, TI: 901ms, flip angle: 8°, field-of-view (FoV): 230 × 230 mm, matrix: 256 × 256, 176 slices, 0.9 mm isotropic voxel resolution. Fast 3-dimensional echoplanar spectroscopic imaging (EPSI) with spin-echo excitation was performed following automatic and manual iterative shimming, with the following parameters: TR: 1550 ms, TE: 17.6 ms, inversion time (TI) for lipid inversion nulling: 198 ms, flip angle: 71°, FoV: 280 × 280 mm, matrix: 50 × 50, 18 slices, 5.6 × 5.6 × 10 mm voxel resolution. The acquisition time for EPSI was 17:48 min. Participants had their body temperature measured in both ears with a Braun Pro 4000 ThermoScan thermometer before and after the MRI.

Image processing

The Metabolite Imaging Data Analysis System (MIDAS)^{44,45} was used to process the whole-brain spectroscopy data as previously described.⁴⁶⁻⁴⁸ Preprocessing is fully automated and includes reconstruction of the spectroscopic images, lipid extrapolation and Gibbs ringing correction, corrections for b0 shifts, Eddy current correction, interpolation to 64×64×32 voxels, smoothing with 5×7mm Gaussian kernel (final voxel size: 5.6×5.6×5 mm), and automated fitting of the CHO, creatine (CR), MI, and NAA peaks with Gaussian line shapes. Apparent brain temperature was calculated with the following formula: $T_{CR} = -102.61(\Delta_{H2O-CR}) + 206.1^{\circ}\text{C}$, where Δ_{H2O-CR} is the difference in resonance frequencies between the water and CR peaks.^{49,50} The metabolite and temperature maps were co-registered with the structural images and the structural images were then non-linearly transformed to Montreal Neurological Institute (MNI) space. Finally, the inverse spatial transform was applied to a modified Automated Anatomical Labeling (AAL) atlas⁵¹ with the PRANA module in MIDAS to obtain atlas regions in subject

space. Mean metabolite levels and temperature were extracted from each ROI for statistical analyses.

The Innate Central Nervous System Immune Response to an
Experimental Immune Challenge in People With Fibromyalgia

Statistical Analysis Plan

NCT04263454

Version Date: 02/16/2023

[name], Professor, Principal Investigator
University of Alabama at Birmingham
[name]

Statistical Analyses

Statistical analyses were conducted with IBM SPSS for Mac version 27. Body temperatures measured in the left and right ear were averaged for each participant. Baseline data were compared between groups using independent-samples t-tests.

Brain metabolite levels were expressed as ratios over the local CR concentration. Brain temperatures below 35.0°C and above 42.0°C were excluded as an additional data quality control measure, as temperatures outside of this range are not physiological. Mixed analyses of variance (ANOVA) were conducted with time as the within-subjects factor (levels: pre-endotoxin, post-endotoxin) and study group as the between-subject factor (levels: FM, healthy control). Endotoxin dose (0.4ng/kg vs 0.3ng/kg) and its interaction with time was added as an additional between-subjects factor, and age and the age-by-time interaction was entered as a covariate of no interest. The effects of interest were the time-by-group interaction (to test whether FM and HC participants exhibited different responses to endotoxin) and the dose-by-time interaction (to test whether participants receiving 0.3ng/kg versus 0.4ng/kg endotoxin exhibited different responses). Significant interactions were followed up with repeated-measures t-tests assessing the effect of time separately for FM patients and HCs. The dependent variables were brain temperature, CHO/CR, NAA/CR, and MI/CR in the 47 brain regions. Because of the small sample size and lack of statistical power, all tests were considered significant at $p < 0.05$. However, all tests meeting a more stringent false discovery rate threshold are highlighted. The false discovery rate threshold of 0.05 yielded a corrected p-value threshold of 0.0113.

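### CHO, MI and NAA are analysed only as ratios to creatine and creatine is never tested, so a creatine change that differs by group or dose could look like a metabolite response or partly mask one

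*SAP*

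**What the plan says.** The Protocol (Methods, Design) names the metabolites themselves as outcomes: "The following were measured with EPSI in 47 brain regions as primary outcomes: brain temperature, CHO, MI, and NAA". Under Image processing it describes "automated fitting of the CHO, creatine (CR), MI, and NAA peaks with Gaussian line shapes", so a CR signal exists for each scan, and it adds: "Mean metabolite levels and temperature were extracted from each ROI for statistical analyses".

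The SAP (Statistical Analyses) sets the scale: "Brain metabolite levels were expressed as ratios over the local CR concentration". Its list of variables is closed: "The dependent variables were brain temperature, CHO/CR, NAA/CR, and MI/CR in the 47 brain regions". CR alone is not on it, nor is any metabolite without the CR denominator. Each variable goes into a mixed ANOVA with time, group, dose and age. The effects of interest are the time-by-group and dose-by-time interactions, and the first is read as showing whether the groups responded differently to endotoxin.

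Neither document plans a check of CR by group, dose or time, a sensitivity analysis on another scale, or a reason for choosing CR as the reference.

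**The concern.** A ratio moves when its numerator rises or when its denominator falls, and the planned variables cannot tell these apart. An immune challenge is given between the two scans, so stability of the denominator is an assumption that needs checking. The three ratios in a region share one CR value, so a single CR effect can appear as three concordant metabolite findings. In the other direction, a real rise in CHO or MI is understated if CR rises with it.

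What is at stake is the name given to a positive result. The aim is to compare metabolite changes between FM and HC, and a ratio interaction alone cannot be assigned to CHO, MI or NAA.

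**Working it through.** The documents give no effect size, variance or power figure for these outcomes, so there is no planned figure to reproduce.

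**1. How many outcomes are involved.** 47 regions × 4 measures = 188; 47 × 3 ratios = 141; 141/188 = 75%. Brain temperature is outside the count. Its formula uses a quantity that "is the difference in resonance frequencies between the water and CR peaks", which is a frequency and not an amount of CR. For the same reason it cannot serve as a check on CR.

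**2. Effect of CR on a ratio.** If the numerator changes by a fraction n and CR by a fraction c, the ratio changes by (1+n)/(1+c) − 1.

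- n = 0, c = −3%: 1/0.97 − 1 = +3.1%
- n = 0, c = −5%: 1/0.95 − 1 = +5.3%
- n = 0, c = −10%: 1/0.90 − 1 = +11.1%
- n = 0, c = +5%: 1/1.05 − 1 = −4.8%
- Masking, n = +10%, c = +5%: 1.10/1.05 − 1 = +4.8%. The rise is roughly halved. It vanishes only when c = n.

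The values of c and n are assumptions; the documents give none.

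**3. Built-in correlation.** Assume equal, independent measurement error with coefficient of variation v in all four signals. On the log scale, a pre/post ratio change has variance 2v² + 2v² = 4v². Two ratios in one region share the CR part, 2v². Their correlation is 2v²/4v² = 0.5 with no biology involved.

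**4. What the SAP model would show.** A simulation with 2,000 runs per setting fitted change scores on group, dose and age. It used N = 25 with 14 and 11 at the two doses (Protocol, Experimental Session) and two-sided p < 0.05. Assumptions outside the documents are an FM/HC split of 13/12, independent errors, and a within-person CV of 3%, 5% or 8%. CHO, MI and NAA were held truly unchanged. Percentages are runs with a significant time-by-group test.

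| CR change | Test | CV 3% | CV 5% | CV 8% |
|---|---|---|---|---|
| −5%, FM only | each ratio | about 49% | about 21% | about 12% |
| −5%, FM only | CR itself | 76% | 36% | 18% |
| −10%, FM only | each ratio | about 98% | about 67% | about 33% |
| −10%, FM only | at least one ratio | 99.9% | 88% | 56% |
| −10%, FM only | all three ratios | 95% | 42% | 11% |
| −10%, FM only | CR itself | 99.9% | 90% | 53% |
| −10%, FM only | unratioed metabolites | 5.3% | 5.7% | 4.9% |
| −10%, both groups | each ratio | 5.6–6.8% | 4.6–5.6% | 4.6–5.7% |

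The last row sets the limit of the point: a CR change shared by both groups leaves the interaction test near its nominal level. The cancellation is not exact, because the ANOVA works on raw ratios. If baseline ratios differed by an assumed 10% between groups, a shared 11.1% shift would leave about 0.10 × 11.1% = 1.1% of baseline in the interaction.

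**5. How precisely CR could be checked.** Under the same assumptions, ignoring dose and age, the 95% half-width for the group difference in CR change is about 2.08 × v × √2 × √(1/13 + 1/12) = 1.18v. That is 3.5%, 5.9% and 9.4% for CVs of 3%, 5% and 8%. A scan-wide scaling error would cancel in a ratio but not in a CR level, so the real interval could be wider and the CR detection rates above are optimistic.

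**The case against.** Several objections have force.

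- **Only differential change matters.** The plan tests interactions, and the within-group pre/post tests run only after a significant one. A reader might infer that any CR change after endotoxin would be reported as a metabolite response. The documents do not support that, and the shared-change row above shows why. This objection stands and limits the point.
- **No CR change is shown.** The count of 141 is of variables sharing a denominator, not of biased results. A reader might infer that the metabolite findings are biased; nothing in either document shows it. This also stands.
- **The ratio is declared.** The SAP states the scale and labels each variable as a ratio, and nothing in it counts agreement among the three as evidence. A reader might infer that primary outcomes were covertly replaced. It is fairer to say that the SAP fixed a scale the Protocol left open. A parallel shift in all three ratios would be a visible clue, but no check for it is planned and it would often be incomplete: at 5% CV, all three were significant in 42% of runs.
- **Water referencing may not be possible.** The Protocol confirms only that the water peak's frequency is used, not that its amplitude was quantified. Water would also be a shared denominator. The remedy must be conditional on this.
- **A non-significant CR test proves little.** The SAP itself concedes low power, and in the simulation the CR test missed a 10% differential fall in 47% of runs at 8% CV. Any rule for attribution must therefore rest on intervals.

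None of this supplies the missing check on the denominator, which is the part that remains.

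**Conclusion.** The point holds for a CR change that differs between FM and HC or between the two doses. Those are the two contrasts the SAP tests, and 75% of the outcomes are exposed to it. Such a change could appear as a CHO, MI or NAA response, partly mask one, and affect up to three outcomes in a region. The direction and form follow from arithmetic alone. The sizes rest on assumed CR changes of 3% to 10%, and the simulated rates also rest on an assumed CV, group split and error structure.

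It is an unaddressed alternative explanation and not a demonstrated bias. It does not undermine the trial, but it governs what a positive metabolite result may be called, and it should be dealt with because the supplementary check needs no new scan.

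**What to change.** Keep the ratios as the main analysis and add the following.

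1. Run the same time-by-group and dose-by-time model on CR in each of the 47 regions. Use water-referenced CR if the water amplitude was acquired, and otherwise the extracted CR level.
2. Report CHO, MI and NAA on that same scale as sensitivity analyses, with estimates and confidence intervals.
3. Label all of these as supplementary and outside the main false discovery rate family. The SAP already reports a realised threshold of 0.0113, so they should also be identified as added afterwards.
4. Describe main results as changes in the ratio to CR. Attribute one to the numerator only where the numerator's own estimate supports it and the CR interval excludes a change large enough to explain the ratio shift. Do not read a non-significant CR test as evidence that CR was stable. Otherwise report a ratio change of undetermined source.

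The cost is SAP text and 47 CR models plus 141 sensitivity models, with no new scan. If water referencing requires amplitudes that were not extracted, some reprocessing is needed or that option falls away. The downside is extra models on noisier values. With 25 participants many CR intervals may be too wide to settle attribution, and the report should then say so.

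### The named pre/post ANOVA uses only complete pairs and the SAP gives no rule for a missing or excluded value; fit the same terms by mixed model on all available scans and report the pairs

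*SAP*

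**What the plan says.** The SAP's Statistical Analyses section sets out the model: "Mixed analyses of variance (ANOVA) were conducted with time as the within-subjects factor (levels: pre-endotoxin, post-endotoxin". Group and dose are between-subject factors, and age is a covariate. The main target is stated as follows: "The effects of interest were the time-by-group interaction (to test whether FM and HC participants exhibited different responses to endotoxin"; the dose-by-time interaction is the other effect of interest. A significant interaction leads to repeated-measures t-tests within each group. One model is run per outcome and region: "The dependent variables were brain temperature, CHO/CR, NAA/CR, and MI/CR in the 47 brain regions". The software is given ("Statistical analyses were conducted with IBM SPSS for Mac version 27"), but the procedure within it is not.

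The same section has one exclusion based on values: "Brain temperatures below 35.0°C and above 42.0°C were excluded as an additional data quality control measure". It does not say whether this acts on voxels or on regional means. It calls the rule additional, yet neither document describes other quality-control exclusions.

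The Protocol, under Design, gives the scan times: "Participants underwent an MRI 1.5 hours before receiving the endotoxin infusion, and 4 hours after". Under Experimental Session it gives the numbers by dose, "0.4ng/kg body weight, N=14, or 0.3ng/kg body weight, N=11", and adds: "The endotoxin dose was reduced to 0.3ng/kg after several participants experienced adverse events following 0.4ng/kg infusions".

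Neither document defines an analysis population, a rule for a participant with one usable value, a count of complete pairs, or a missing-data sensitivity analysis.

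**The concern.** With two time points, the time-by-group test is a between-group comparison of change scores. A participant with one value has no change score, so the classical ANOVA drops her from that model along with the value she does have. A paired t-test does the same.

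There are two ways to lose a value.

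- **Temperature exclusion.** It acts on a primary outcome, and an exclusion at one scan can cost the good value at the other. The set analysed may then differ between the 47 temperature models without the reader knowing.
- **A post-endotoxin scan that is not completed.** The Protocol reports adverse events after the infusion, and the second scan comes 4 hours later with a 17:48-minute spectroscopic acquisition. If such a loss occurred, it could be related to dose and to the size of the response, which are what the two interactions examine.

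Loss confined to one group or one dose passes straight into the corresponding interaction. With 25 participants, each lost pair is 1/25 = 4% of the data.

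**Working it through.** The documents give no missing-scan count, FM/HC split, SD, pre-post correlation or power calculation, so there is no planned figure to reproduce. What follows shows ranges under stated assumptions.

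**From the documents**
- Infused: 14 + 11 = 25.
- Models: 4 outcomes × 47 regions = 188. The temperature rule bears on 47 of them; 188 − 47 = 141 are metabolite ratios.
- Between-subject terms on the change score: intercept, group, dose, age, so error df = N − 4.

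**Assumed:** 13 participants in the group that loses scans; equal SDs at the two scans; pre-post correlation ρ of 0.5 or 0.7.

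**1. Pairs left after temperature exclusion.** If each scan fails independently with probability q, expected complete pairs = 25(1 − q)².

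| q | Expected pairs |
|---|---|
| 2% | 24.0 |
| 5% | 22.6 |
| 10% | 20.3 |

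**2. Power for an interaction of 1.0 SD of change.** Noncentral t with two-sided α = 0.05, near-equal groups and noncentrality d√(n₁n₂/N).

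| Pairs | Error df | Power | Effect detectable with 80% power |
|---|---|---|---|
| 25 | 21 | 66% | 1.18 SD |
| 22 | 18 | 60% | 1.26 SD |
| 20 | 16 | 56% | 1.34 SD |

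**3. Precision recovered by keeping pre-only participants.** Let n be the group size and m the number with both scans. In units of the measurement variance, and treating the covariance as known, the variance of the mean change is
- complete pairs: 2(1 − ρ)/m
- likelihood model on all scans: (1 − ρ²)/m + (1 − ρ)²/n

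For n = 13, m = 10, ρ = 0.5: complete pairs 1/10 = 0.1000; all scans 0.75/10 + 0.25/13 = 0.0942. The reduction is 5.8%.

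| Pre-only of 13 | Reduction, ρ = 0.5 | Reduction, ρ = 0.7 |
|---|---|---|
| 1 | 1.9% | 1.2% |
| 3 | 5.8% | 3.5% |
| 5 | 9.6% | 5.8% |

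**4. Bias when loss depends on the baseline value.** Suppose 3 of 13 are lost and average 1 SD above their group at baseline. The other 10 then average 3 × 1/10 = 0.3 SD below it. The slope of change on baseline is ρ − 1 = −0.5, so the completers' mean change is biased by (−0.3)(−0.5) = +0.15 SD. Retaining the baseline values in a likelihood model removes this bias, because the loss is explained by observed data.

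**5. Bias when loss depends on the response itself.** Simulation with 13 participants and a true mean change of 0.8 SD of change. Loss follows an adverse-event propensity correlated 0.5 with change.

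| Lost | Mean change among completers |
|---|---|
| 1 | 0.73 |
| 2 | 0.67 |
| 3 | 0.62 |

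If the three lost are the three largest responders (worst case), the estimate is 0.43, a shortfall of 0.37. Half of that, 0.185, gives 0.615, which agrees with the 0.62 row. The mixed model does not remove this bias.

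**The case against.** The strongest reply is that no missing scan is documented. The Protocol describes both scans without exception and links the adverse events only to the change of dose. A reader might infer that the results describe only women who tolerated the challenge, or that anyone failing quality control is removed from the study. The documents do not support either inference. A participant who had an adverse event and completed the second scan stays in. A temperature exclusion acts within a temperature model and leaves her other models intact. The SAP justifies the rule as removing non-physiological readings, which is a measurement problem and not evidence about tolerance. If it is applied to voxels before averaging, a region may keep its value. All of this stands.

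Complete-pair handling is inferred from the method's name, since the SPSS procedure is not identified. That is correct, but the inference is the ordinary one for an ANOVA with paired follow-up tests, and the SAP offers nothing to displace it.

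The remedy can also be called weak: with two time points it recovers little precision, and it does not cure loss driven by the unobserved response. This too stands, and it is why counts and a conditional sensitivity analysis must accompany the model. It is no reason to keep the complete-pair method: the alternative matches it on the interaction tests when data are complete, and improves on it when loss is explained by baseline.

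**Conclusion.** The point holds as a gap in the analysis method with a conditional risk attached. The named procedures need both values, the SAP provides nothing else, and its own exclusion rule can leave a participant with one value in the temperature models. The further step, to bias from women who could not complete the second scan, is possible but not shown.

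The size for this trial cannot be derived and may be zero. Under the assumptions above, losing 3 of 13 in one group costs 0.15 SD if loss follows baseline. It costs about 0.18 SD (0.80 − 0.62) if loss follows a moderate correlate of response, and 0.37 SD at worst. The mixed model removes the first and not the other two. Its gain in precision is about 1% to 10% of the variance. The change should be made because it is cheap and because the counts would settle whether bias can arise at all; nothing here shows that the reported tests are wrong.

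**What to change.** 1. **Model.** Fit time, group, dose, age and their interactions with time as a linear mixed model with an unstructured 2×2 covariance on all available scans (SPSS MIXED, with small-sample degrees of freedom). Include participants with one valid value. Take the within-group time effects from this model in place of the paired t-tests.
2. **Exclusion rule.** State whether the temperature limits apply to voxels or regional means, and list any other quality-control exclusions.
3. **Counts.** Report the numbers infused, with a second scan, and with complete pairs, by group, dose and outcome/region, with reasons for each loss.
4. **Conditional sensitivity analysis.** If any post scan is missing after an adverse event, impute it over a stated range of shifts in both directions, since the documents give no expected direction for any outcome. Report where the interaction conclusion changes. If none is missing, say so and omit this step.

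**Cost.** SAP wording and a re-run in the same software, with no new data or participants. With no missing values the interaction tests are unchanged. The within-group effects may differ somewhat from the paired t-tests because they would be adjusted for dose and age.

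### The only follow-up rule for a significant interaction splits by FM and HC, so a significant dose-by-time result is either broken down by the wrong factor or not followed up at all

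*SAP*

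**What the plan says.** The SAP, Statistical Analyses, declares two interactions. One concerns diagnosis: "The effects of interest were the time-by-group interaction (to test whether FM and HC participants exhibited different responses to endotoxin"). The other concerns dose: "the dose-by-time interaction (to test whether participants receiving 0.3ng/kg versus 0.4ng/kg endotoxin exhibited different responses"). The next sentence is the only follow-up rule: "Significant interactions were followed up with repeated-measures t-tests assessing the effect of time separately for FM patients and HCs". It does not say which of the two interactions it applies to.

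On the model, the SAP says: "Endotoxin dose (0.4ng/kg vs 0.3ng/kg) and its interaction with time was added as an additional between-subjects factor". Age and its interaction with time are covariates. No dose-by-group-by-time term is described.

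On outcomes: "The dependent variables were brain temperature, CHO/CR, NAA/CR, and MI/CR in the 47 brain regions". On the threshold: "Because of the small sample size and lack of statistical power, all tests were considered significant at" p < 0.05. The false discovery rate cut-off only marks results for emphasis. It does not decide which interactions are followed up.

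The Protocol, Experimental Session, gives the dose groups as "0.4ng/kg body weight, N=14, or 0.3ng/kg body weight, N=11" and explains how they arose: "The endotoxin dose was reduced to 0.3ng/kg after several participants experienced adverse events following 0.4ng/kg infusions". Neither document gives the dose split within FM and HC, and neither describes a test of time within a dose level.

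**The concern.** A follow-up test should break an interaction down along the factor that produced it. Splitting by FM and HC does this for time-by-group. It does not do so for dose-by-time, because each diagnostic group contains a mixture of doses and its t-test estimates a dose-weighted average change.

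Two things are at stake:

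- **Location of the dose effect.** The FM and HC tests do not say whether the change happened at 0.4 ng/kg, at 0.3 ng/kg, or in opposite directions at the two doses.
- **Stray group patterns.** The rule sets an FM p-value beside an HC p-value for regions where time-by-group was not significant. One may fall below 0.05 and the other not, through sampling variation or because the groups differ in dose mix. That contrast is easily read as a group difference that the designated test did not find.

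**Working it through.** The plan gives no figure on this point to reproduce. The finding rests on the wording; the arithmetic below gives its scale.

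**1. Text check.** Two interactions are declared, and one rule is given, naming only FM and HC. With no dose-by-group-by-time term described, nothing in the model gives a reason to split a dose effect by diagnosis.

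**2. Number of possible triggers.** 4 measures × 47 regions = 188 dose-by-time tests. If all nulls hold, 188 × 0.05 = 9.4 are expected to trigger follow-up. Correlation between regions does not change this expectation, but it does affect the spread around it.

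**3. What the FM and HC tests estimate.** Suppose the mean change depends on dose only: δ₀.₄ and δ₀.₃, with no group difference. The expected change in a group is (n₀.₄ × δ₀.₄ + n₀.₃ × δ₀.₃) / (n₀.₄ + n₀.₃). The dose totals are 14 and 11 (N = 25). The cell counts are not in the documents, so three splits are assumed, in the order FM 0.4 / FM 0.3 / HC 0.4 / HC 0.3. With δ₀.₄ = 1 SD and δ₀.₃ = 0:

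- 7/6/7/5: FM 7/13 = 0.54 SD; HC 7/12 = 0.58 SD
- 9/4/5/7: FM 9/13 = 0.69 SD; HC 5/12 = 0.42 SD
- 4/8/10/3: FM 4/12 = 0.33 SD; HC 10/13 = 0.77 SD

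The last two splits give unequal group averages from dose mix alone. The t-tests drop the model's dose adjustment.

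**4. How often the two tests disagree.** In each of 10,000 simulated data sets per scenario, the pre-to-post change was regressed on group, dose and age. With two time points, this is equivalent to the time interactions in the mixed ANOVA. There was no true group-by-time effect, and alpha was 0.05 two-sided (the SAP does not state sidedness). The percentages are among cases where dose-by-time was significant and time-by-group was not. Monte Carlo error is about one percentage point in the last row and smaller in the others.

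Exactly one of FM and HC significant:

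| Change at 0.4, 0.3 (SD) | 7/6/7/5 | 9/4/5/7 | 4/8/10/3 |
|---|---|---|---|
| 1, 0 | 42.8% | 51.1% | 60.7% |
| 1.2, 0.2 | 46.2% | 57.2% | 65.9% |
| +0.5, −0.5 | 3.8% | 7.5% | 13.6% |
| 0, 0 (chance trigger) | 5.5% | 5.3% | 7.6% |

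With opposite changes, neither test was significant in 96.1%, 92.4% and 86.2% of cases. The dose effect is real, but the follow-up shows nothing.

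**5. The same cases followed up by dose.** With changes of 1 and 0 SD, the within-dose t-test was significant in about 99% of cases at 0.4 ng/kg and 4–5% at 0.3 ng/kg, so it located the effect. With +0.5 and −0.5 SD, it was significant in 57–58% at 0.4 ng/kg and 47–51% at 0.3 ng/kg.

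**The case against.** The strongest reply is that the sentence names the two levels of the group factor, so it probably describes the time-by-group follow-up only, with a plural because there are many outcomes. This reading is plausible and cannot be excluded. Under it, no dose interaction triggers an FM or HC test. What remains is an omission: one of two declared effects of interest has no stated follow-up.

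A reader might infer that the dose question goes unanswered. The documents do not support that. The SAP asks whether responses differ between two doses. With two doses and two time points this is a one-degree-of-freedom contrast; the interaction test answers it, and the model estimates give its direction. Only the change at each dose is missing.

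A reader might also infer that the plan will produce false group claims. It can, but the SAP assigns the group question to the time-by-group test and describes the t-tests as assessing time. Nothing says that a significant and a non-significant result will be reported as a group difference.

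Finally, a reader might put disagreement between the two t-tests at 50%. If both have power p and are independent, disagreement is 2p(1 − p), which peaks at p = 0.5. It is 9.5% at p = 0.05, 32% at 0.8 and 18% at 0.9. The documents give no power, and 50% does not describe the 9.4 chance triggers. For those the simulation gives 5–8%, or at most about 9.4 × 0.076 = 0.7 outcomes on average.

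**Conclusion.** The concern holds as a moderate defect in the follow-up rule. Read literally, the SAP breaks a significant dose-by-time interaction down by the wrong factor; read narrowly, it does not break it down at all. The sentence needs changing either way.

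Up to 188 tests are exposed, with about 9.4 chance triggers expected under the complete null. The rate of 'one group only' patterns is not known for this trial. The ranges of about 5–8% for chance triggers and about 4–66% with a true dose effect rest on assumed cell counts, effect sizes, equal variances and no relation between age and change. They illustrate what can happen and are not estimates for these data.

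The severity stops at moderate because both interaction tests, the model and the outcomes stay as they are. Only a post hoc step and its interpretation are affected. The excess of chance triggers itself comes from testing each outcome at an uncorrected 0.05, which is a separate issue.

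**What to change.** Replace the follow-up sentence with text to this effect:

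- A significant time-by-group interaction is followed by the time effect within FM and within HC.
- A significant dose-by-time interaction is followed by the time effect within each dose level.
- Group-specific time effects are not reported as group differences unless time-by-group is significant.

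Preferably, take these as simple effects from the fitted model, with confidence intervals, rather than from separate t-tests. Within-dose effects are then adjusted for age and group, and within-group effects for age and dose. A table of dose by group would let readers judge the overlap.

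The cost is one SAP sentence and a re-run of the affected follow-ups on existing data. There are two downsides to state. The within-dose groups are small (14 and 11), and dose changed during the study after adverse events rather than by randomisation, so these estimates are descriptive. Following up by dose also gives no protection against a false trigger: with no effect at all, the simulated within-dose t-tests were significant in 25–34% of triggered cases at 0.4 ng/kg and 29–35% at 0.3 ng/kg, because those cases were selected for a large dose contrast.
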